2.4. Sequence of Planned Analyses

2.4.1. Planned Interim Analyses

Interim analyses for safety are planned for this trial (see Section 13). The interim analyses will be performed by an external, independent, unblinded reporting team.

The results will be reviewed by an IDMC comprised of external medical and statistical experts that will provide recommendations to the Sponsor. The IDMC charter provides details regarding procedures to protect the scientific integrity of the trial, conduct of the IA, and dissemination of results.

An interim efficacy/futility analysis was planned in each indication (UC and CD) when approximately 50% of patients in the indication have completed the 14-week primary efficacy readout time point or had the opportunity to do so. Due to accelerated recruitment, at the time that the data cut for this IA would have taken place, all participants in both indications had already been randomized. Given the duration of the treatment period in the trial, 14 weeks, Teva decided that the efficacy/futility IA would not be conducted as it would be impractical and have limited utility.

2.4.2. Final Analyses and Reporting

After the database has been locked for final analysis, all final analyses identified in this SAP will be performed.

The randomization codes will not be unblinded for final analysis until this SAP has been approved and issued and the database has been locked, including all external efficacy data (e.g. endoscopy scores) that are required for the primary and secondary efficacy analysis.

2.4.3. Analyses Out of the Scope of This SAP

Population Pharmacokinetic, Pharmacodynamic, and Pharmacokinetic/Pharmacodynamic Analysis: A pop-PK analysis will be performed, and, if feasible, a PK/PD analysis of relevant pharmacodynamic variables and/or exposure-response analysis of relevant efficacy or safety endpoints may be performed. The analyses may be reported in a separate pharmacometrics report and may have separate pre-specified analysis plan. These analyses may not be reported in the clinical study report (CSR) and are out of the scope of the current SAP.

Pharmacogenetic Analysis: Exploratory analyses may be undertaken to describe the relationship between genetic polymorphisms (single-nucleotide polymorphisms) and treatment effects of TEV-48574. These analyses may be reported in a separate report and may have a separate pre-specified analysis plan. These analyses may not be reported in the CSR and are out of the scope of the current SAP.

Biomarker Analysis: In addition to the analysis of hsCRP, fecal calprotectin, albumin, free and total TEV-48574 defined in this SAP, additional exploratory analyses may be undertaken to investigate the treatment effects of TEV-48574 on hsCRP, fecal calprotectin, autoantibodies, and other potential TL1A-mediated serum biomarkers. These additional analyses may be reported in a separate report and may have a separate pre-specified analysis plan. These analyses may not be reported in the CSR and are out of the scope of the current SAP.

2.5. Sample Size and Power Considerations

A total trial sample size of approximately 240 participants is planned, with 120 participants (40 participants per dose arm) each for the 2 indications of UC and CD.

The sample size does not include participants that were randomized to the 1800 mg Q2W treatment group prior to Protocol Amendment 03 with Revision 01.

Assumptions:

The clinical remission and endoscopic response rates assumed in the sample size and related operating characteristics computations are as follows:

- Clinical remission rates in UC group: 8% for placebo; 30% for TEV-48574 groups, respectively
- Endoscopic response rates in CD group: 12% for placebo; 34% for TEV-48574 groups, respectively

Additional scenarios for remission (UC), response rates (CD) are assumed as outlined in [Table 2](#) to investigate the operating characteristics.

Table 2: Remission (UC), Response (CD) Rates Scenarios for Clinical Trial Simulations

Scenario	Indication	Placebo (%)	TEV-48574 450 mg Q2W (%)	TEV-48574 900 mg Q2W (%)
Null	UC	8	8	8
	CD	12	12	12

Table 2: Remission (UC), Response (CD) Rates Scenarios for Clinical Trial Simulations (Continued)

Scenario	Indication	Placebo (%)	TEV-48574 450 mg Q2W (%)	TEV-48574 900 mg Q2W (%)
Intermediate Efficacy	UC	8	20	20
	CD	12	25	25
Efficacy	UC	8	30	30
	CD	12	34	34
Efficacy-high dose only	UC	8	8	30
	CD	12	12	34

CD=Crohn's disease; Q2W=every 2 weeks; UC=ulcerative colitis.

Operating Characteristics:

Simulation-based operating characteristics for the analysis of the primary efficacy variable using a Bayesian Beta Binomial model are presented in [Table 3](#). This model uses a posterior probability cutoff of ≥ 0.90 to declare success at the final analysis.

Table 3: Operating Characteristics of Final Analysis

	UC			CD		
	TEV-48574 450 mg Q2W	TEV-48574 900 mg Q2W	At least 1 dose	TEV-48574 450 mg Q2W	TEV-48574 900 mg Q2W	At least 1 dose
Null	7.9%	7.9%	13.5%	9.6%	9.6%	16.1%
Intermediate efficacy	61.1%	61.1%	77.3%	59.3%	59.3%	75.9%
Efficacy	91.0%	91.0%	97.6%	87.1%	87.3%	95.5%
Efficacy-high dose only	7.9%	91.1%	91.1%	9.6%	87.2%	87.3%

CD=Crohn's disease; Q2W=every 2 weeks; UC=ulcerative colitis.

Beta-Binomial model with non-informative prior Beta(1,1); decision rule for declaring difference from placebo is based on having a posterior probability of ≥ 0.90 .

Note: Operating characteristics based on 500,000 simulations.

These simulations demonstrate that the probability of a false positive result, i.e., declaring success for at least 1 dose within each indication under the null assumption for both doses, is $\leq 16\%$ for each indication, while the probability of declaring success for at least 1 dose within each indication under the efficacy assumption for both doses is $\geq 95\%$.

Since the analysis is done separately for each dose and each indication, the probability of demonstrating efficacy in one dose is not affected by the other dose. Moreover, no inflation of the Type 1 error rate is expected in hypothetical discordant scenarios where TEV-48574 is effective in one indication but not in the other.

As a supplemental analysis, a frequentist logistic regression analysis with 40 participants per dose per indication would provide at least 90% power using a Mantel-Haenszel test with a 1sided

nominal Type I error rate of 10% . However, the interpretation for this frequentist analysis is different from that of the Bayesian analysis as it is an inference on the sample space as opposed to the parameter space.

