Table 14: Safety Stopping Rules – Example 3: Pooled TEV-48574 vs placebo, different numbers of participants, stopping criterion: 90%

Total N	Number of Placebo Participants With Event	Number of TEV-48574 Participants With Event	Probability of TEV-48574 >Placebo
36	0/7	8/29	0.912
36	0/9	7/27	0.936
36	1/7	13/29	0.914
36	1/9	10/27	0.909
72	0/16	8/56	0.919
72	0/18	7/54	0.919
72	1/16	13/56	0.916
72	1/18	11/54	0.906

APPENDIX 3. COMPARISON OF PRIMARY ANALYSIS MODEL BETWEEN PROTOCOL AMENDMENT 02 AND PROTOCOL AMENDMENT 04

This section presents a comparison of the major changes in the primary analysis model between Protocol Amendment 02 and Protocol Amendment 04.

The statistical analysis method for the primary analysis was changed from an Emax dose-response- model, which was planned when the study design incorporated 3 treatment arms of TEV-48574 active doses and a placebo arm, to a pairwise comparison approach, primarily due to the removal of 1 active treatment arm. With only 2 active dose arms and a placebo arm, the Emax model would not yield robust or precise estimates for characterizing the dose-response relationship and is no longer appropriate to assess the primary objective of the Phase 2 dose range finding study, which is to characterize the efficacy of 2 doses of TEV-48574 in patients with moderate- to-severe UC or CD.

Additionally, the previous analysis method included a Bayesian borrowing approach that relied on an assumption that both indications, UC and CD, will be concordant (drug is either effective in both indications or not effective in both indications). This is now changed to a simplified Bayesian Beta-Binomial model with no borrowing, and the model is fit separately within each indication, where each dose is compared with placebo. This approach makes minimum assumptions on the dose-response curve shape and the data structure.

Operating characteristics of this approach, for the planned sample size, were considered adequate for a Phase 2 study (See Section 2.5). For UC, for each dose the Type I error rate is 8%, and the probability to declare a dose as successful at the end of the study under the assumption of efficacy is 91%; for CD, for each dose the Type I error rate is approximately 10%, and the probability to declare a dose as successful at the end of the study under the assumption of efficacy is 87%.

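### The at-least-90% power stated for the supplementary Mantel-Haenszel test holds for UC but not for CD, where the plan's own rates give about 87%

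*SAP*

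**What the plan says.** Section 2.5 plans 240 participants, "with 120 participants (40 participants per dose arm) each for the 2 indications of UC and CD". It assumes UC remission of 8% on placebo and 30% on each active dose. For the other indication it gives: "Endoscopic response rates in CD group: 12% for placebo; 34% for TEV-48574 groups, respectively".

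Table 3 then gives the chance of declaring success under the primary Beta-binomial rule when both doses work. For a single dose this is 91.0% in UC and 87.1% to 87.3% in CD. Appendix 3 repeats the CD value: "the probability to declare a dose as successful at the end of the study under the assumption of efficacy is 87"%.

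After the table, Section 2.5 turns to the supplementary frequentist analysis, which "with 40 participants per dose per indication would provide at least 90% power using a Mantel-Haenszel test", one-sided, at a "nominal Type I error rate of 10"%. One figure is given, and it is not limited to UC.

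Section 6.2.3 plans the Cochran-Mantel-Haenszel (CMH) tests as comparisons of each active dose with placebo, run separately in UC and CD.

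**The concern.** The two indications have the same assumed difference, 22 percentage points, but CD starts from a higher placebo rate. The binomial variance is therefore larger and power is lower at the same sample size. Table 3 shows this for the Bayesian rule, with 91% in UC against 87% in CD. A single figure of at least 90% for a frequentist test of the same two proportions, at a matching 10% level, does not fit that pattern.

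The stake is how a negative CD result on the supplementary test would be read. A reader who relies on the sentence would assume at most a 10% chance of missing the planned effect. The sentence also suggests that the supplementary test is more powerful than the primary rule in CD.

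**Working it through.** **Inputs**, all from Section 2.5 except the last:
- n = 40 per arm in each indication
- UC 8% vs 30%; CD 12% vs 34%
- one-sided level 0.10, so the critical value is z = 1.2816
- each dose against placebo, separately by indication (Section 6.2.3)

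**Step 1: reproduce the plan's own figures.** Let x be the number of placebo responders and y the number of active responders, each from 0 to 40. For each of the 41 × 41 = 1,681 outcomes, apply the rule Prob(p_d > p_0) ≥ 0.90 with Beta(1,1) priors, and weight the outcome by its binomial probability.

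| | UC exact | UC Table 3 | CD exact | CD Table 3 |
|---|---|---|---|---|
| Null, one dose | 7.87% | 7.9% | 9.56% | 9.6% |
| Null, at least 1 dose | 13.53% | 13.5% | 16.05% | 16.1% |
| Efficacy, one dose | 91.03% | 91.0% | 87.17% | 87.1% / 87.3% |
| Efficacy, at least 1 dose | 97.56% | 97.6% | 95.45% | 95.5% |

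The method agrees with the SAP's simulations to within about 0.1 point.

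**Step 2: the Mantel-Haenszel test.** With t = x + y, the unstratified statistic without continuity correction is

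z = (y − t/2) / √V, where V = 40² · t · (80 − t) / (80² · 79).

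Reject when z ≥ 1.2816. Exact power over the same 1,681 outcomes:
- UC: 0.9105, about 91.1%
- CD: 0.8718, about 87.2%

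**Step 3: cross-check by the pooled normal formula**, power = Φ[(Δ − 1.2816 · SE₀) / SE₁].
- UC: Δ = 0.22, mean rate 0.19. SE₀ = √(2 × 0.19 × 0.81 / 40) = 0.0877. SE₁ = √((0.08 × 0.92 + 0.30 × 0.70) / 40) = 0.0842. The argument is (0.22 − 0.1124) / 0.0842 = 1.278, so power is 89.9%.
- CD: Δ = 0.22, mean rate 0.23. SE₀ = √(2 × 0.23 × 0.77 / 40) = 0.0941. SE₁ = √((0.12 × 0.88 + 0.34 × 0.66) / 40) = 0.0908. The argument is (0.22 − 0.1206) / 0.0908 = 1.094, so power is 86.3%.

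**Step 4: does another version of the test reach 90% in CD?** Exact CD power is 87.2% for the score and likelihood-ratio tests, 87.9% for the unpooled difference test, and 81.2% for the continuity-corrected Mantel-Haenszel test and for Fisher's test. None reaches 90%.

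**Step 5: consistency with Table 3.** At 40 per arm, the Bayesian rule and the uncorrected Mantel-Haenszel test decide differently in only 4 of the 1,681 outcomes: (x, y) = (0, 2), (1, 4), (36, 39) and (38, 40). These carry almost no probability at the CD efficacy rates (0.8718 against 0.8717). So 87% for one procedure and at least 90% for the other cannot both be right.

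**The case against.** The best defence is that the sentence never names the event to which the power refers. Grammatically, the words about dose and indication describe the 40 participants, not the power. If the event were success for at least one of the two doses, exact Mantel-Haenszel power would be 97.6% in UC and 95.4% in CD, and the statement would be true. This does not rescue it. Where Section 2.5 means that event it says so, as in its false-positive statement about "declaring success for at least 1 dose within each indication under the null assumption for both doses", and the power sentence does not. Section 6.2.3 plans each dose against placebo. Pooling the doses (93.2% in CD by the pooled formula) or combining the indications (98.7%) would also exceed 90%, but both depart from that planned analysis.

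A second defence is that stratification or covariate adjustment may change power. That is possible, but the SAP gives no covariate effects from which to derive a gain of about 3 points.

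The defence on importance stands. The analysis is supplementary and its level nominal. Success is decided only by the posterior probability in Section 6.2.2, and the correct CD figure for that rule appears in both Table 3 and Appendix 3. Section 2.4.1 also records that all participants had already been randomized when the interim efficacy analysis was dropped.

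The 16% bound on false positives is essentially a rounding matter: the exact CD value is 16.05% and Table 3 prints 16.1%.

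**Conclusion.** The stated power is wrong for CD. For each dose versus placebo it is about 87%, roughly 3 points below the stated minimum, and the miss probability is about 13% rather than at most 10%. For UC the statement is supported: 91.1% exactly, and 89.9% by the normal approximation, which rounds to 90%.

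This rests on the plan's assumed rates, 40 evaluated participants per arm, and an unstratified test without continuity correction. The SAP does not say whether a correction applies. With one, power would be 85.8% in UC and 81.2% in CD.

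A reader might infer that the trial is underpowered in CD or that its primary operating characteristics are misreported. The documents do not support that: the primary figures reproduce, and Appendix 3 accepts 87% as adequate for Phase 2. A reader might also infer that the claim fails in both indications. On the uncorrected form of the test that the SAP names, it does not.

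Severity is minor: one sentence about a supplementary analysis, with no effect on any estimate, decision rule or conclusion.

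**What to change.** In Section 2.5, replace the single figure with one per indication and name the event and the test: approximately 91% power in UC and 87% in CD for each dose versus placebo (unstratified Mantel-Haenszel test, one-sided nominal 10%). Saying that no continuity correction is used would make the figures reproducible. In the same edit, the upper bound of 16% on the false-positive probability may be aligned with the 16.1% in Table 3.

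The cost is one or two sentences of wording. The CD figure becomes about 3 points less favourable and then agrees with Table 3 and Appendix 3. The sample size, primary analysis and success criterion do not change.

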3. ANALYSIS SETS

3.1. Intent-to-Treat Analysis Set

The intent-to-treat (ITT) analysis set for each indication (UC or CD) will include all randomized participants.

In the ITT analysis set, participants will be categorized by treatment to which participants were randomized, regardless of which treatment they actually received.

Data collected from participants after treatment discontinuation will be included in the ITT analysis set.

3.2. Modified Intent-to-Treat Analysis Set

The modified intent-to-treat (mITT) analysis set for each indication (UC or CD) is a subset of the ITT analysis set including only participants who receive at least 1 dose of placebo, TEV-48574 450 mg Q2W or TEV-48574 900 mg Q2W.

In the mITT analysis set, participants will be categorized by treatment to which participants were randomized, regardless of which treatment they actually received.

3.3. Safety Analysis Set

The safety analysis set for each indication (UC or CD) will include all randomized participants who receive at least 1 dose of IMP.

In the safety analysis set, participants will be categorized by treatment actually received, regardless of the treatment to which they were randomized, unless otherwise specified.

Rules for assignment of treatment in case of mixed actual treatments:

- If a participant received placebo throughout the entire treatment period, then the actual treatment is placebo.
 - if a participant received a loading dose of TEV-48574 and received placebo in all other induction doses, the participant will be categorized to the TEV-48574 450 mg Q2W treatment arm.
- Otherwise (participant received at least 1 induction dose of TEV-48574), actual treatment is TEV-48574.
 - in case of kit mix-up, the participant will be categorized according to the highest induction dose (450 mg Q2W, 900 mg Q2W, or 1800 mg Q2W) that they received anytime during the trial

Rule for assignment of treatment in case of loading dose only (no induction doses):

- If a participant received a loading dose of TEV-48574 and had no induction doses, the participant will be categorized to the TEV-48574 450 mg Q2W treatment arm.

3.4. Immunogenicity Analysis Set

The immunogenicity analysis set will include all participants in the safety set who receive TEV-48574 and who have at least 1 reportable immunogenicity result.

3.5. Pharmacokinetic Analysis Set

The pharmacokinetic (PK) analysis set will include all participants in the safety set who receive TEV-48574 and who have at least 1 reportable serum concentration result.

Participants with kit mix-ups will be excluded from the PK analysis set.

4. GENERAL ISSUES FOR DATA ANALYSIS

4.1. General

Descriptive statistics for continuous variables include n, mean, standard deviation (SD), standard error (SE), median, minimum, and maximum. Descriptive statistics for categorical variables include participant counts and percentages, missing category will be displayed as appropriate.

In case of discrepancies between stratification factors as recorded in the clinical database and as recorded in the randomization system, the stratification factors as recorded in the clinical database will be used for all summaries and analyses.

4.2. Specification of Baseline Values

The baseline value is the last observed data before the first dose of trial drug, unless otherwise noted.

4.2.1. Baseline Value – MMS, CDAI, and PRO2

See [Appendix 4](#) for derivation of baseline CDAI and PRO2-CD. The same window for participant-reported outcomes will be applied to baseline MMS and PRO2-UC.

Derived baseline MMS and derived baseline CDAI will not be used for eligibility or for definition of response for assignment to maintenance/re-induction in study 20038.

Derived baseline MMS and derived baseline CDAI will be used for sensitivity analysis only.

4.2.2. Baseline Value – ECG

The baseline value for electrocardiogram (ECG) variables is the mean of the triplicate values at the screening visit. The baseline value for the ECG finding (normal, abnormal) is the worst case finding of the triplicate findings.

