4.4. Trial Days and Visits

For by-visit summaries, if there are multiple assessments at a postbaseline visit then the last non-missing assessment at that visit will be used for the summary (this includes scheduled and unscheduled assessments).

Trial days are numbered relative to the first day of trial drug administration. The start of treatment (Day 1) is defined as the date on which a participant takes the first dose of trial drug, as recorded on the clinical database. Days will be numbered relative to treatment start (i.e., ..., -2, -

1, 1, 2, ...; with day 1 being the first day of trial drug administration and day –1 being the day before the first day of trial drug administration).

4.5. Classification of Intercurrent Events – Initiation or Dose Increase of Inflammatory Bowel Disease Medications

The intercurrent events of initiation or dose increase medications used to treat the IBD will be classified as follows:

Medication	ICE Classification
5-ASA; sulfasalazine (SSZ)	Important protocol deviations, including use or changes in other medications (treatment policy)
Immunosuppressants – other than MTX	Important protocol deviations, including use or changes in other medications (treatment policy)
Immunosuppressants – MTX	Rescue medication
Systemic corticosteroids (IV, PO, IM, suppository)	Rescue medication
Advanced IBD therapies (biologics, JAK inhibitors, S1P inhibitors)	Rescue medication

As described in the primary estimand (Section 1.2), ICEs classified as “Rescue medication” will be handled using the composite strategy, i.e., the participant will be reported as non-remitter/non-responder; ICEs classified as “Important protocol deviations, including use or changes in other medications” will be handled using the treatment policy, i.e., data after the ICE will be used regardless of the ICE. These strategies will be applied to all response/remission efficacy endpoints.

All participants with initiation or dose increase of IBD medications will be reviewed in the statistical data review meeting prior to DBL, where the classification will be confirmed on a case-by-case basis.

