Shifts (normal, abnormal not clinically significant, and abnormal clinically significant) from baseline to each visit that this is measured, and from baseline to overall (anytime) will be summarized using participant counts for the investigator interpretation. For overall result interpretation the worst postbaseline finding for the participant (the abnormal finding if there are both normal and abnormal findings) will be used in the summaries.

Summary statistics for ECG variables will be presented at baseline and each visit that it is measured. Actual values and changes from baseline to each visit will be summarized using descriptive statistics.

The incidence of potentially clinically significant abnormal values will be summarized using descriptive statistics with the criteria specified in [Table 10](#). Note that to qualify as potentially clinically significant abnormal, a value needs to meet both criteria below, if applicable: e.g., have a value beyond the criterion value and a change of at least the magnitude specified in the change relative to baseline column. A listing of potentially clinically significant ECG results will be presented.

Table 10: Criteria for Potentially Clinically Significant Abnormal ECG

ECG Test	Criterion Value	Change Relative to Baseline
PR Interval	≥200 msec	Increase of at least 25% from baseline
QRS Duration	≥110 msec	Increase of at least 25% from baseline
QTcF Interval	≥450 msec and <500 – male or ≥460 msec and <500 – female	≥30 and <60 msec increase from baseline
	≥450 msec and <500 – male or ≥460 msec and <500 – female	≥60 msec increase from baseline
	≥500 msec	≥30 and < 60 msec increase from baseline
	≥500 msec	≥60 msec increase from baseline

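### Unless post-baseline triplicate ECGs are also reduced to their worst finding, which the SAP does not state, the by-visit ECG shift table compares the worst of three readings with one

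*SAP*

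**What the plan says.** Section 4.2.2 gives two ECG baselines. For numeric variables, "The baseline value for electrocardiogram (ECG) variables is the mean of the triplicate values at the screening visit". For the categorical interpretation, "The baseline value for the ECG finding (normal, abnormal) is the worst case finding of the triplicate findings".

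Section 4.4 sets the general rule for summaries presented visit by visit: "if there are multiple assessments at a postbaseline visit then the last non-missing assessment at that visit will be used for the summary", adding that "this includes scheduled and unscheduled assessments". ECG is not exempted.

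Section 8.6 plans two shift tables for the investigator's interpretation, "from baseline to each visit that this is measured, and from baseline to overall (anytime) will be summarized using participant counts". A worst-case rule after baseline is given only for the second: "For overall result interpretation the worst postbaseline finding for the participant" is used. Nothing in 8.6 or elsewhere says how several findings at one post-baseline visit are combined, and the SAP does not say whether post-baseline ECGs are single or triplicate.

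**The concern.** A shift table is informative only if the category on each side is derived in the same way. Here the baseline has three chances to be called abnormal, while the visit, read as written, has one. Two things follow whenever the three screening readings can disagree.

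- Baseline is abnormal more often than a visit even if nothing has changed, so the table drifts towards apparent improvement.
- A participant with one abnormal reading out of three at screening starts in an abnormal row and can no longer contribute a normal-to-abnormal shift.

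Change from baseline in ECG findings is a listed safety measure in Section 1.1, and Section 8.6 reports these shifts as participant counts, which readers take at face value within an arm.

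**Working it through.** The SAP states no ECG rate, so there is no figure of its own to reproduce. The direction of the effect follows from the rules; its size needs assumptions.

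**Inputs**
- From the SAP: baseline is the worst of 3 (4.2.2); the visit is taken as one reading (4.4, as written).
- Assumed: a participant's chance p that any one reading is called abnormal follows a Beta distribution with mean m and within-participant correlation ρ, so a = m(1/ρ − 1) and b = (1 − m)(1/ρ − 1). Given p, readings are independent. The same correlation applies within the triplicate and between visits. No drug effect.

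**Formulas.** Let Eₖ be the mean of (1 − p)ᵏ, that is, the product over j = 0 to k − 1 of (b + j)/(a + b + j).
- Abnormal at baseline: 1 − E₃
- Abnormal to normal: E₁ − E₄
- Normal to abnormal: E₃ − E₄
- One reading on each side, each direction: E₁ − E₂
- Worst of three on each side, each direction: E₃ − E₆

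**Example: m = 0.20, ρ = 0.5**, so a = 0.2 and b = 0.8.
- E₁ = 0.8; E₂ = 0.8 × 1.8/2 = 0.72; E₃ = 0.72 × 2.8/3 = 0.672; E₄ = 0.672 × 3.8/4 = 0.6384; E₆ = 0.6384 × (4.8/5) × (5.8/6) = 0.5924
- Abnormal at baseline: 1 − 0.672 = 32.8%, against 20.0% at the visit
- Apparent improvement: 0.8 − 0.6384 = 16.2%
- Apparent worsening: 0.672 − 0.6384 = 3.4%
- Symmetric rules: 0.8 − 0.72 = 8.0% each way (single against single); 0.672 − 0.5924 = 8.0% each way (worst against worst)

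In an arm of 40, the planned size per indication, that is about 6.5 participants improving and 1.3 worsening, instead of about 3.2 each way.

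**Range, no drug effect**

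| Abnormal per reading | Correlation | Improve | Worsen | Single vs single, each way |
|---|---|---|---|---|
| 10% | 0.3 | 14.3% | 3.5% | 6.3% |
| 10% | 0.5 | 9.4% | 2.1% | 4.5% |
| 10% | 0.7 | 5.3% | 1.1% | 2.7% |
| 10% | 0.9 | 1.7% | 0.3% | 0.9% |
| 20% | 0.5 | 16.2% | 3.4% | 8.0% |
| 30% | 0.7 | 11.9% | 2.3% | 6.3% |

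Over 10–30% abnormal and correlation 0.3–0.7, normal-to-abnormal shifts are about 45% to 64% fewer than with one reading on each side. The ends are 1 − 3.47/6.30 = 45% (10%, 0.3) and 1 − 2.26/6.30 = 64% (30%, 0.7).

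**If the drug doubles the odds of an abnormal reading** (20%, 0.5): as written, 5.5% worsen and 12.4% improve; with one reading on each side, 11.8% and 5.9%. The active-placebo difference in new abnormalities is 5.5 − 3.4 = about 2.2 points before rounding, against 11.8 − 8.0 = 3.8.

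**The case against.** **Section 4.4 may not be about triplicates.** Its remark on scheduled and unscheduled assessments fits repeat assessments at a visit at least as well as replicates within one ECG recording. A reader might infer that the SAP definitely discards two of three post-baseline readings. The text does not establish that. On the other reading, however, the SAP has no rule for combining a post-baseline triplicate, and if visits have a single ECG the mismatch is there regardless. The gap stands either way.

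**The rule is common to all arms.** This is right. The table is not tilted towards active treatment, and a reader who infers that would be mistaken.

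**Concealed harm is too strong a reading.** In the no-effect case every normal-to-abnormal shift is noise, so fewer of them also means fewer false signals. In the doubled-odds example the active-to-placebo ratio of new abnormalities is higher as written (5.5/3.4 = 1.64 unrounded) than with single readings (11.8/8.0 = 1.47). Dividing each difference by √[p₁(1 − p₁) + p₀(1 − p₀)] gives 0.074 against 0.090, a loss of about 17%, whereas the drop in percentage points suggests about 40%. What stands is that each arm's absolute counts mislead and the contrast is somewhat blunted.

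**Other displays cover ECG safety.** Section 8.6 also plans the anytime shift on the worst post-baseline finding, numeric changes from the triplicate mean, the Table 10 criteria for PR, QRS and QTcF, and a listing. An abnormality missed at one visit can surface there. The point is therefore limited to the by-visit table.

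**Two baseline levels against three in the shift table.** A reader might see a contradiction between 4.2.2 and 8.6. Section 5.9 already summarises the screening interpretation at three levels, so the parenthesis in 4.2.2 is best read as shorthand.

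**Conclusion.** The point holds for the by-visit ECG shift table. As written, or wherever a visit has a single ECG, it compares worst-of-three with one reading. With no drug effect it then shows more improvement than worsening in every arm and undercounts new abnormalities at a visit.

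The direction needs only that screening readings sometimes disagree. The size rests wholly on assumed variability: 16.2% against 3.4% at 20% abnormal and correlation 0.5, falling to 1.7% against 0.3% at 10% and correlation 0.9. If triplicates are taken at visits and reduced to their worst finding, the bias disappears, but the SAP does not state that rule.

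This is a correctable flaw in a descriptive safety table with no test or decision attached. It does not touch the primary conclusion, and the documents do not support a claim that the ECG safety evaluation as a whole would miss harm.

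**What to change.** In Sections 4.2.2 and 8.6, state that the ECG finding is derived by the same rule on both sides of the by-visit shift table.

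- Where the visit ECG is triplicate, use the worst of the three findings at that visit, as at baseline, and say that this overrides 4.4.
- Where the visit ECG is single, use one pre-specified screening reading as the baseline for this table, for example the last of the triplicate, in line with the general baseline rule in 4.2. A majority-of-three baseline would not do: against one reading it gives 7.7% worsening and 6.1% improvement with no effect (20%, 0.5), a smaller bias in the opposite direction.
- Keep the worst-case baseline, if wanted, for the anytime shift.

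The cost is SAP wording and a derivation line, with no new data, and it can be settled before unblinding. The small downside is that the by-visit and anytime tables may then use different baselines, which a footnote should state.
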